9.5. Sample Size Determination

The planned total sample size for the study is up to approximately 781 randomized participants.

Main Cohort (Cohort A)

A sufficient number of participants will be screened to achieve a total of approximately 416 randomized participants, with 380 participants randomly assigned to ponsegromab 300 mg Q4W and placebo Q4W in approximately a 1:1 ratio, plus an additional 36 participants randomly assigned to ponsegromab 100 mg Q4W and 200 mg Q4W in approximately a 1:1 ratio. Participants will be randomized initially in a 1:1:1:1 ratio to all four treatment arms (until approximately 72 participants are randomized), followed by a 1:1 ratio to the 300 mg Q4W and placebo arms only. This planned number of randomized participants is expected to ensure completion of the Main Cohort (Cohort A) of approximately 161 evaluable participants in the 300 mg Q4W and placebo Q4W treatment arms and approximately 15 evaluable participants in the 100 mg and 200 mg Q4W treatment arms, assuming a discontinuation rate of 15% (if this rate is higher, or there is a high rate of non-compliance, more participants may be randomized to ensure the required number of evaluable participants).

The sample size in the ponsegromab 300 mg Q4W and placebo arms is based

CCI

CCI

The sample size in the ponsegromab 100 mg and 200 mg Q4W arms has been chosen empirically to provide sufficient data to gain a preliminary understanding of the PK/PD relationship in this population, and is not based on the primary endpoint.

Open-Label, PK Cohort (Cohort B)

Approximately 20 additional participants will be randomly assigned to open-label ponsegromab 100 mg, 200 mg and 300 mg Q4W in approximately a 1:2:2 ratio. This sample size has been chosen empirically to provide sufficient evaluable participants (approximately 15) to adequately evaluate the PK of ponsegromab following repeated SC administration to participants with HF and elevated circulating GDF-15 concentrations, assuming a 15% discontinuation rate (if this rate is higher, or there is a high rate of non-compliance, more participants may be randomized to ensure the required number of evaluable participants).

Cohort C (optional)

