A sufficient number of participants will be screened to achieve a total of approximately 195 randomized participants, with 130 participants randomly assigned to ponsegromab 100 mg Q4W and 65 to placebo Q4W in approximately a 2:1 ratio. This planned number of randomized participants is expected to ensure completion in Cohort C of approximately 110 evaluable participants in the 100 mg Q4W and 55 in the placebo Q4W treatment arms, assuming a discontinuation rate of 15% (if this rate is higher, or there is a high rate of non-compliance, more participants may be randomized to ensure the required number of evaluable participants). This sample size of 165 completers is based on the primary efficacy endpoint and, when combined with the completing 100 mg Q4W and placebo Q4W participants in the Main Cohort (Cohort A), gives similar acceptable Operating Characteristics to those for the 300 mg Q4W arm in the Main Cohort.

CCI

Cohort D (optional)

Approximately 100 participants will be randomly assigned to ponsegromab 300 mg Q4W or placebo in approximately a 1:1 ratio in Cohort D. This sample size has been estimated based on the number of participants being screened for Cohort C and the anticipated screen-fail rate. The actual sample size may be lower or higher than estimated, with a maximum of approximately 150 total participants in this cohort. Enrollment into Cohort D will stop approximately when enrollment into Cohort C stops.

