**2.3. Study Design**

This is a Phase 2, parallel-group, randomized, double-blind, placebo-controlled study to evaluate the effect of ponesegromab (PF-06946860) on HRQL, physical activity, safety, and circulating biomarkers in adult participants with HF and elevated circulating GDF-15.

For the Main Cohort (Cohort A), Cohort C, and Cohort D, following the 56-day screening period to confirm eligibility, the study will include a 22-week treatment period and a 10-week follow-up period for a total study duration of 32 weeks not including the screening period.

Approximately 416 participants will be enrolled into the Main Cohort (Cohort A) and randomized to one of 3 doses of ponesegromab (100 mg [n=18], 200 mg [n=18], or 300 mg [n=190]) or to matched placebo (n=190). Approximately 195 additional participants may be enrolled into optional Cohort C and randomized in a 2:1 ratio to either 100 mg ponesegromab (n~130) or to matched placebo (n~65). The participants in optional Cohort C will allow for a more comprehensive evaluation of the safety and efficacy of the ponesegromab 100 mg dose level compared to placebo. For each of these cohorts, blinded study drug will be administered SC Q4W for a total of 6 doses during the 22 week treatment period.

Participant randomization will be stratified based on CCI

CCI

KCCQ-23 CSS: <45 or ≥45.

The primary endpoint for the study is the change from baseline at Week 22 in KCCQ-23 CSS, an HRQL PRO instrument.

[figure not shown]
Approximately 100 participants (maximum of approximately 150) who meet all eligibility criteria for Cohorts A and C, except the requirement for serum GDF-15 concentration CCI CCI pg/mL, may be enrolled into the optional Cohort D and randomized in a 1:1 ratio to

either 300 mg ponsegromab ( $n \sim 50$ ) or to matched placebo ( $n \sim 50$ ), administered SC Q4W for a total of 6 doses during the 22 week treatment period. Participant randomization in Cohort D will be stratified by KCCQ-23 CSS:  $<45$  or  $\geq 45$ . The purpose of this optional cohort is for a supportive assessment of efficacy and safety endpoints across the spectrum of GDF-15 concentrations in participants with HF.

[figure not shown]

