### **3.2.5. Incidence of TEAEs, TESAEs, abnormal laboratory results, and vital signs (All Cohorts [A, B, C and D])**

#### **3.2.5.1. Adverse Events**

An adverse event is considered a Treatment-Emergent Adverse Event (TEAE) if the event started during the effective duration of treatment. All events that start on or after the first dosing day and time/start time, if collected, but before the last dose plus the lag time will be flagged as TEAEs. The lag time is defined by the Pfizer standard of 365 days post last dose of IP. The algorithm will not consider any events that started prior to the first dose date.

A Treatment-Emergent Serious Adverse Event (TESAE) is a TEAE which also meets the definition of a Serious Adverse Event (SAE).

A 3-tier approach will be used to summarize TEAEs. Under this approach, TEAEs are classified into 1 of 3 tiers: -

Tier 1 events: These are prespecified events of clinical importance and are maintained in a list in the product's Safety Review Plan (or similar, e.g. Safety Surveillance Review Plan).

Tier 2 events: These are events that are not tier 1 but are "common." A Medical Dictionary for Regulatory Activities (MedDRA) preferred term (PT) is defined as a Tier 2 event if there are at least 5% of participants reporting the event in either the placebo group or combined over the ponssegromab treatment groups.

Tier 3 events: These are events that are neither Tier 1 nor Tier 2 events.

Potential immunogenic AEs including potential cases of angioedema, anaphylaxis, hypersensitivity, delayed hypersensitivity reactions and events potentially meeting the Sampson criteria (as defined in Appendix 3) will be medically evaluated in a blinded manner throughout the study to determine whether or not they are immune reactions and possibly related to study drug and categorized as per guidance as: 1) Hypersensitivity, 2) Anaphylaxis, 3) Angioedema, 4) Delayed immune response and / or 5) Cytokine Release syndrome.

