#### 6.2.5. Incidence of TEAEs, TSEAEs, abnormal laboratory results and vital signs (All Cohorts [A, B, C and D])

For analysis of adverse events (AEs), laboratory abnormalities and vital signs *the Main Cohort (Cohort A) and Cohort C will be reported combined*, with data from the same treatment group combined across cohorts; *the open-label, PK cohort (Cohort B) will be reported separately; Cohort D will be reported separately*. The safety analyses will use the corresponding safety analysis sets, defined in Section 4.

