##### 6.2.5.1. Adverse Events

Adverse events (Tier 1, 2 and 3 AEs as described in Section 3.2.5.1) will be summarized by treatment group (including ponesegromab combined) and overall, in accordance with sponsor reporting standards. The adverse events will be sorted in descending frequency within a system organ class. If applicable, subject discontinuations due to adverse events will be detailed and summarized.

Incidence and severity of TEAE and TSEAE tables will additionally be produced ('All causality' and 'Treatment related', separately) to summarise the total number of adverse events by preferred term, which will be reported by treatment group (including ponesegromab combined) and overall.

TEAEs classed as Tier 2 events (except for the PK cohort) will each be tabulated by treatment group (including ponesegromab combined). The number and percentage of participants will be presented, along with the risk difference (and 95% confidence interval) between each dose of ponesegromab and placebo. No adjustment for multiplicity will be used.

Tier 2 TEAEs (except for the PK cohort) will also be presented graphically in two-panel plots; the left panel will present the proportions of TEAEs observed in a dose group of ponesegromab (including ponesegromab combined) and separately placebo, while the right panel will display the 95% confidence interval for the risk differences for each TEAE. A vertical line corresponding to the value of 0 will be added to the right-hand plot. Each panel will be paged by treatment group of ponesegromab.

Tier 2 TEAE outputs will be ordered in descending point estimate of risk difference within System Organ Class. If two or more events have the same frequency they will be sorted alphabetically by preferred term. Footnotes will be included on the tables to provide proper interpretation of confidence intervals and to describe how the comparison was conducted, e.g. "Confidence intervals are not adjusted for multiplicity and should be used for screening purposes only. 95% Confidence intervals are provided to help gauge the precision of the estimates for Risk Difference. Risk Difference is computed as ponesegromab versus placebo."

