### 6.2.5.3. Vital Signs

Absolute values and changes from baseline in vital signs (supine systolic and diastolic blood pressure and pulse rate) will be summarized by treatment group (including ponesegromab combined) and overall, and timepoint, according to sponsor reporting standards.

In addition (except for the PK cohort), changes from baseline will be analyzed using an MMRM model, as described in Section 5.2.3. The MMRM model will be fitted to the change from baseline at all post-treatment timepoints up to Week 22 using the safety analysis set (as defined in Section 4). Additional terms for baseline LVEF, log GDF-15 concentrations from SV1 and baseline log NT-proBNP may be fitted in the model. The Main Cohort (Cohort A) and Cohort C will be reported combined, with data from the same treatment group combined across cohorts; Cohort D will be reported separately. Note that cohort will be included as a term in the statistical model when analysis includes data from more than one cohort.

Maximum increase/decrease from baseline for supine systolic and diastolic blood pressures and maximum increase/decrease from baseline for supine pulse rate will be summarized by treatment group (including ponesegromab combined) and overall, according to sponsor reporting standards.

Maximum absolute values and changes from baseline for supine vital signs will also be summarized descriptively by treatment group (including ponesegromab combined) and overall, using categories as defined in Appendix 5. Numbers and percentages of participants meeting the categorical criteria will be provided. All planned and unplanned post dose timepoints will be counted in these categorical summaries. All values meeting the criteria of potential clinical concern will be listed.

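### Adverse-event risk differences merge Cohorts A and C with no stated cohort stratification, so any difference in event rates between the cohorts would leak into the dose contrasts, most of all 100 mg versus placebo

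*SAP*

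**What the plan says.** SAP 6.2.5 reports Cohorts A and C together for adverse events, laboratory abnormalities and vital signs, "with data from the same treatment group combined across cohorts". For Tier 2 events, SAP 6.2.5.1 gives numbers and percentages "along with the risk difference (and 95% confidence interval) between each dose of ponesegromab and placebo". Neither section names a cohort stratum, a weighting scheme or an adverse-event table by cohort.

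Elsewhere, data merged in the same way are adjusted. The vital-signs section (SAP 6.2.5.3) states: "Note that cohort will be included as a term in the statistical model when analysis includes data from more than one cohort". Efficacy approach 3 in SAP 5.2, which combines A and C, also adds cohort to its models.

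The two cohorts allocate very differently. Cohort A is planned as "100 mg [n=18], 200 mg [n=18], or 300 mg [n=190]) or to matched placebo (n=190" (SAP 2.3). Cohort C is planned with "130 participants randomly assigned to ponsegromab 100 mg Q4W and 65 to placebo Q4W in approximately a 2:1 ratio" (Protocol 9.5).

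**The concern.** The ratio of 100 mg to placebo is 18:190 in Cohort A and 130:65 in Cohort C. When arms are merged across cohorts with such different ratios, the merged comparison is no longer a within-cohort randomized comparison. If background incidence of an event differs between cohorts, part of that difference appears in the dose-versus-placebo contrast even when the drug does nothing.

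Later calendar time is one way such a gap could arise. SAP Section 1 dates the amendment that added Cohort C to 18 Jul 2024. SAP 7.2.1 shows that the Cohort A interim efficacy population had been randomized by 07 May 2024.

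What is at stake is the reading of the 100 mg safety data, which Cohort C is meant to strengthen. The error has opposite signs for 100 mg and 300 mg, so a cohort gap could also look like a difference between doses. SAP 6.2.5.1 orders Tier 2 output by the point estimate of the risk difference, so a shift also affects which events are listed first.

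**Working it through.** **Inputs.** Arm sizes come from SAP 2.3 and Protocol 9.5. Event rates by cohort are not in the documents and are assumed. Planned randomized numbers stand in for the safety set.

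**The plan's own figures.** Cohort A: 18 + 18 + 190 + 190 = 416, as stated. Cohort C: 130 + 65 = 195, as stated. With 15% discontinuation, 130 × 0.85 = 110.5 and 65 × 0.85 = 55.25, matching the stated 110 and 55.

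**Share of each merged arm that comes from Cohort C.**

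- 100 mg: 130/(18 + 130) = 130/148 = 87.8%
- Placebo: 65/(190 + 65) = 65/255 = 25.5%
- 200 mg and 300 mg: 0%
- All ponsegromab doses combined: 130/356 = 36.5%

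**Leak formula.** Suppose there is no drug effect, with incidence pA in Cohort A and pC in Cohort C. An arm with Cohort C share w has expected incidence pA + w(pC - pA). The merged risk difference is therefore (w_dose - w_placebo) × (pC - pA).

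- 100 mg: 0.878 - 0.255 = +0.623 of the gap
- 200 mg and 300 mg: 0 - 0.255 = -0.255 of the gap
- Combined ponsegromab: 0.365 - 0.255 = +0.110 of the gap

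**Spurious risk difference (percentage points) by assumed gap pC - pA.**

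| Gap | 100 mg | 300 mg |
|---|---|---|
| 0 | 0 | 0 |
| 5 | +3.1 | -1.3 |
| 10 | +6.2 | -2.5 |

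The signs reverse if Cohort C has the lower incidence.

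**Direct check at pA = 10%, pC = 15%.**

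- Placebo: (190 × 0.10 + 65 × 0.15)/255 = 28.75/255 = 11.3%
- 100 mg: (18 × 0.10 + 130 × 0.15)/148 = 21.3/148 = 14.4%
- 300 mg: 10%

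The contrasts are +3.1 and -1.3 points, as the formula gives.

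**How often the 100 mg interval would exclude zero with no drug effect.** This used 400,000 simulated trials per scenario, assumed incidences of 5% to 30%, and Wald 95% intervals.

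- Merged estimate: 5.2% with no gap, 13% to 18% with a 5-point gap, 28% to 43% with a 10-point gap.
- Cohort-stratified Mantel-Haenszel estimate: 5.3% to 5.6% in every scenario, with mean bias of zero.

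**Precision cost of stratifying.**

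- 100 mg: the Mantel-Haenszel weights are 18 × 190/208 = 16.44 and 130 × 65/195 = 43.33, total 59.78. The merged equivalent is 148 × 255/403 = 93.65. At equal incidence the standard error ratio is √(93.65/59.78) = 1.25. At 10% incidence that is 3.9 points against 3.1. The simulated scenarios gave increases of about 20% to 26%.
- 300 mg: Cohort C has no 300 mg participants, so that stratum gets zero weight and placebo falls from 255 to 190. The ratio is √[(1/190 + 1/190)/(1/190 + 1/255)] = 1.07.

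**The case against.** The strongest reply is that the bias is conditional. It is zero unless incidence differs between cohorts, and no rates are given. Cohorts A and C share eligibility criteria, visit schedule and stratification factors, and Cohort C may never be enrolled. All of this stands, and it is why the size is given as a range that includes zero.

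The merged estimator is also an inference. SAP 6.2.5.1 defers to sponsor reporting standards that are not in the documents, and those could specify stratification. The supportable statement is that none is stated, although the same SAP states cohort adjustment for vital signs and efficacy.

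The SAP calls safety analysis exploratory and limits the intervals to screening. That lowers the consequence. But those caveats concern multiplicity and causal claims, and neither removes confounding by cohort.

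A reader might also infer that the Tier 2 rule hides a 300 mg signal, because it requires "at least 5% of participants reporting the event in either the placebo group or combined" over the ponsegromab groups: 17/190 (8.9%) at 300 mg alone is 17/356 = 4.8%. The example is fragile. One further event at 100 mg or 200 mg gives 18/356 = 5.06%, which qualifies. Placebo must also be below 5%, events in all three tiers are still summarized by treatment group, and prespecified important events are Tier 1 regardless. The threshold needs no change on this ground.

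**Conclusion.** The point holds as a conditional weakness that is cheap to correct. If Cohort C is enrolled at the planned size and the adverse-event comparison is merged as written, 62% of any between-cohort difference in incidence enters the 100 mg contrast, and 25% enters the 200 mg and 300 mg contrasts with the opposite sign. For scale, an assumed 5-point gap produces a 3.1-point error for 100 mg, about one standard error at 10% incidence.

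Three stronger readings are tempting, and the documents do not support them.

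- That cohort differences will appear as drug effects: no event rates are given, so only the leak fraction is known.
- That Cohort C uses different sites or reporting practices: neither document says so. Later calendar time is the mechanism that the dates support.
- That a 300 mg safety comparison is a stated purpose of Cohort C: Protocol 4.1 gives its purpose as evaluation of 100 mg against placebo, and it has no 300 mg arm.

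A reversal of the apparent dose order is possible in principle, but it has not been shown against any assumed true dose effect.

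**What to change.** In SAP 6.2.5.1, state that Tier 2 risk differences and 95% confidence intervals from merged Cohorts A and C are stratified by cohort with Mantel-Haenszel weights. For 200 mg and 300 mg this reduces to comparison with Cohort A placebo. Keep the pooled counts and percentages for display, and describe the estimator in the table footnote. If Cohort C is not enrolled, the rule has no effect.

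The cost is SAP wording and a programming option, with no change to data collection. The standard error rises by about 20% to 26% for 100 mg and about 7% for 300 mg.

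The fix is partial. Protocol 9.5 says: "Participants will be randomized initially in a 1:1:1:1 ratio to all four treatment arms (until approximately 72 participants are randomized"; after that, only 300 mg and placebo are assigned. About 72/4 = 18 of the 190 Cohort A placebo participants are therefore concurrent with the Cohort A 100 mg and 200 mg arms, and the other 172 (91%) come later. Stratifying by cohort leaves that calendar-time imbalance in place, including in the whole of the 200 mg contrast. The SAP should acknowledge it.

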It should be recognized that most studies are not designed to reliably demonstrate a causal relationship between the use of a pharmaceutical product and an adverse event or a group of adverse events. Except for select events in unique situations, studies do not employ formal adjudication procedures for the purpose of event classification. As such, safety analysis is generally considered as an exploratory analysis and its purpose is to generate hypotheses for further investigation. The 3-tier approach facilitates this exploratory analysis.

TEAE classed as Tier 1 events (except for the PK cohort) will be tabulated by treatment group. The number and percentage of participants, reporting events listed in the pre-specified Tier 1 list, will be tabulated by treatment group (with ponesegromab treatment groups combined only) and overall, and by severity. Note that Tier 1 events are not planned to be presented graphically due to the small number of expected events.

Note that Tier 1 and 2 events will not be presented for the open-label, PK cohort (Cohort B).

Injection site reactions (ISR) will also be summarized by treatment group (including ponesegromab combined) and overall, in accordance with sponsor reporting standards. The ISRs will be sorted in descending frequency within a system organ class. Incidence and severity of ISR tables will additionally be produced ('All causality' and 'Treatment related', separately) to summarise the total number of ISR by preferred term, which will be reported by treatment group (including ponesegromab combined) and overall.

Potential immunogenic AEs will be summarized by medical evaluation category (see Section 3.2.5.1) and treatment groups (including ponesegromab combined) and overall.

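### Tier 1 adverse events have no planned risk difference or CI versus placebo, and their dedicated table pools all ponsegromab doses, whereas Tier 2 events get a per-dose comparison

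*SAP*

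**What the plan says.** SAP 3.2.5.1 sorts treatment-emergent events into three tiers. Of Tier 1 it says "These are prespecified events of clinical importance"; the list itself is kept in the Safety Review Plan. The next tier is defined to exclude the first: "Tier 2 events: These are events that are not tier 1 but are" common. Common means "at least 5% of participants reporting the event in either the placebo group", or in the ponsegromab groups taken together.

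SAP 6.2.5.1 then sets the output for each tier:

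- **All tiers.** The section opens with a summary of Tier 1, 2 and 3 events by treatment group, with a combined ponsegromab column and an overall column. Incidence and severity tables by preferred term follow, with the same columns.
- **Tier 2.** Number and percentage by treatment group and combined, "along with the risk difference (and 95% confidence interval) between each dose of ponesegromab and placebo", plus two-panel plots. A footnote says that the intervals are unadjusted and are for screening only.
- **Tier 1.** One sentence reads "TEAE classed as Tier 1 events (except for the PK cohort) will be tabulated by treatment group". The next says that the number and percentage of participants will be "tabulated by treatment group (with ponesegromab treatment groups combined only) and overall, and by severity". No risk difference or interval is named. The only reason given for showing less concerns plots: "Tier 1 events are not planned to be presented graphically due to the small number of expected events".

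**The concern.** The tiers should put the most analytic attention on the events the sponsor singled out in advance. For the comparison with placebo the order is reversed: an event gets an estimate and an interval if it is common and not on the Tier 1 list, and neither if it is on the list. Because the tiers are exclusive, a listed event that is also common cannot get the estimate through Tier 2.

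The dedicated table also pools 100, 200 and 300 mg. A reader who goes to it for the prespecified events sees a single active column, in which a harm related to dose is averaged with lower-dose participants. The two Tier 1 sentences do not sit easily together either: one promises a table by treatment group, and the next limits the active arms to a combined column. A programmer could reasonably build either.

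**Working it through.** The documents give no Tier 1 event rate, power or interval width, so there is no stated figure to reproduce. The check has three parts.

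**1. What is planned for each tier (SAP 6.2.5.1)**

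| Output | Tier 1 | Tier 2 |
|---|---|---|
| Per-dose counts in the general AE tables | yes | yes |
| Per-dose counts in the tier's own table | unclear in the first sentence, combined only in the second | yes |
| Risk difference and 95% CI versus placebo | none stated | each dose |
| Plot | no, few events expected | yes |
| Severity breakdown in the tier's own table | yes | not stated; severity is tabulated for all TEAEs |

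The differences that matter are rows 2 and 3.

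**2. Size of the pooling effect**

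Safety data from Cohorts A and C are combined (SAP 6.2.5). The planned numbers come from SAP 2.3:

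- 100 mg: 18 + 130 = 148
- 200 mg: 18
- 300 mg: 190
- Ponsegromab pooled: 148 + 18 + 190 = 356
- Placebo: 190 + 65 = 255

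If the lower doses have the placebo rate and only 300 mg has an excess d, the pooled excess is d × n(300 mg) / n(pooled):

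- With Cohort C: 190/356 = 0.53
- Without Cohort C: 190/(18 + 18 + 190) = 190/226 = 0.84
- Cohort D, reported separately: 300 mg is its only active dose, so pooling changes nothing.

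**3. When does listing an event as Tier 1 remove a comparison?**

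Only if the event would otherwise qualify as Tier 2. With Cohort C, 5% of 356 is 17.8, so 18 participants on ponsegromab are needed; or 5% of 255 is 12.75, so 13 on placebo.

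Two illustrations follow. All counts are assumed. The intervals are Newcombe score intervals for a difference: with p the observed proportion and (l, u) its 95% Wilson limits, lower = d − √[(p₁ − l₁)² + (u₂ − p₂)²] and upper = d + √[(u₁ − p₁)² + (p₂ − l₂)²].

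| Assumed counts | 300 mg v placebo | Pooled v placebo | Tier if not listed |
|---|---|---|---|
| 15/190 at 300 mg, 3/166 at lower doses, 5/255 placebo | 5.9 points (2.0 to 10.8) | 18/356 v 5/255: 3.1 points (−0.04 to 6.1) | Tier 2 (18/356 = 5.1%) |
| 11/190 at 300 mg, 2/166 at lower doses, 3/255 placebo | 4.6 points (1.2 to 9.0) | 13/356 v 3/255: 2.5 points (−0.2 to 5.1) | Tier 3 (13/356 = 3.7%; 3/255 = 1.2%) |

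In the first row, listing costs the event a planned comparison. In the second it costs nothing relative to the unlisted case, since no risk difference is planned for Tier 3 either; the pooled Tier 1 table still roughly halves the excess. As written, the plan prints none of these four intervals for a Tier 1 event.

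Few events do not rule out an interval: 2/190 v 0/255 gives 1.1 points (−0.6 to 3.8).

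**The case against.** **Tier 1 events are already shown by dose.** The first sentence of SAP 6.2.5.1 names Tier 1 and promises summaries by treatment group. This stands. A reader might infer from the Tier 1 paragraph that dose-level data on these events are withheld, or that a 300 mg harm would be hidden. The documents do not support that: an excess would be visible as per-dose counts beside placebo, and a difference could be worked out by hand. Those tables cover Tier 2 as well, however, and Tier 2 still gets an estimate on top.

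**The comparison is lost only above the cut-off.** This also stands. A reader might infer that listing an event always strips it of a comparison. It does so only at 5% or more on placebo or on ponsegromab combined, and the SAP expects few Tier 1 events. The list is in a document not supplied here, so it cannot be said whether any listed event would get that far.

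**The two Tier 1 sentences can be reconciled.** The first may describe a table by group, and the second a separate table by severity with doses combined. That reading is possible, but the text does not say so. It calls for clarification either way.

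**Safety analysis is exploratory and descriptive, and an external committee monitors it.** This is true, but it applies equally to Tier 2, which gets intervals with a screening footnote. The small expected number of events is offered only as the reason for omitting plots.

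**The main named product risks are covered by dose.** Injection site reactions and potential immunogenic events have their own per-dose summaries. This limits what is at stake but does not supply a comparison for the Tier 1 list.

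**Conclusion.** The point holds as a specific gap in reporting. No between-group estimate or interval is planned for Tier 1 events, and their dedicated table combines the doses. Tier 2 events get a per-dose risk difference with a 95% CI. The SAP gives no reason for that difference, only for the missing plots. The omission is a matter of silence in the text rather than an explicit exclusion.

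The size depends on Cohort C, which is optional. In the pooled table a 300 mg-only excess shows at 53% of its size with Cohort C enrolled as planned and at 84% without it, assuming that the lower doses behave like placebo. The event counts above only illustrate this; with rarer events both intervals can include zero (6/190 v 3/255: 2.0 points, −0.8 to 5.6; pooled 7/356 v 3/255: 0.8, −1.7 to 3.0).

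The point does not show that any safety signal would be missed, and it has no bearing on the efficacy analysis. It is an inexpensive improvement worth making.

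**What to change.** In the Tier 1 paragraph of SAP 6.2.5.1:

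1. Remove the restriction to the combined ponsegromab group, and merge the two sentences into one unambiguous specification.
2. Tabulate Tier 1 events, each event and the list as a whole, by ponsegromab dose and combined, keeping the severity breakdown.
3. Add the risk difference versus placebo with a 95% CI, for each dose and combined, by a score or exact method suited to small counts.
4. Reuse the Tier 2 footnote stating that the intervals are unadjusted and for screening only.

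Plots can stay omitted for the reason already given. The cost is a few lines of SAP text and one extra table from data already collected. The drawback is wide intervals when events are few, above all for 200 mg with 18 participants.
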